8.2 NONINVESTIGATIONAL MEDICINAL PRODUCT(S)

Not applicable.

8.3 BLINDING PROCEDURES

8.3.1 Methods of blinding

Refer to [Section 10.5](#) for suspected unexpected adverse drug reaction requiring unblinding by the Sponsor.

In the double-blinded period of the study, avalglucosidase alfa and alglucosidase alfa will be provided as open-label supplies.

For blinding purposes, the on-site preparation of avalglucosidase alfa and/or alglucosidase alfa will therefore be performed by an independent unblinded pharmacist or an independent unblinded designee at the investigational site. The unblinded pharmacist or the unblinded designee should not be involved in activities that could be biased by the knowledge of the treatment assignment (eg, AE assessments, access to PD data) and will not disclose any information to anyone and ensure to maintain blinding condition of the study.

Each treatment kit will be labeled with a number generated by a computer program according to Sanofi procedure. The treatment numbers will be obtained by the unblinded pharmacist or the

unblinded designee at the time of patient randomization and subsequent patients' visits scheduled via centralized treatment allocation system (interactive response technology [IRT]).

In accordance with the double-blind design of the first blinded treatment period, study patients, Investigators and study site personnel, except for the unblinded pharmacist or the unblinded designee, will remain blinded to study treatment and will not have access to the randomization (treatment codes) except under circumstances described in [Section 8.3.2](#). The unblinded pharmacist or the unblinded designee is not allowed to disclose any unblinded information to the blinded study site team and therefore should not take part to any discussion regarding AE assessments for the patients, except to give information in a blinded manner on the preparation of the IMP (eg, preparation steps order well followed, confirmation of the usual visual aspect of the IMP once diluted).

Additional measures will be taken to ensure blinding of the patients (see pharmacy manual for details).

8.3.2 Randomization code breaking during the study

In case of an AE, the code should only be broken in circumstances when knowledge of the IMP is required for treating the patient.

Code breaking can be performed at any time by using the proper module of the IRT and/or by calling any other phone number provided by the Sponsor for that purpose. If the blind is broken, the Investigator should document the date, time of day, and reason for code breaking.

The code-breaking can also be performed by contacting the "24-hour alert system". A patient card, including the relevant "24-hour alert system" telephone number will be provided to every patient who will participate in the study.

If the code is broken, the patient must withdraw from IMP administration. Please refer to [Section 10.3](#) of the protocol for details on handling of patient treatment discontinuation.

At the facilities where the systemic drug concentration measurements, ADAs and selected biomarkers are determined, the samples will be analyzed prior to data base lock leading to unblinding of responsible bioanalysts. Bioanalysts are excluded from the clinical trial team. One programmer may be unblinded to prepare the dataset for population PK analysis. The procedure detailing the process to maintain blind beyond the programmer is described in a separate Sanofi quality document.

8.4 METHOD OF ASSIGNING PATIENTS TO TREATMENT GROUP

Upon confirmation by the Investigator or Subinvestigator (if appropriately delegated) that the patient meets all eligibility criteria and completion of the screening and baseline assessments, eligible patients will be randomized as described below.

Treatment assignment and randomization will be performed using a centralized treatment allocation system/IRT. During the double-blind period, approximately 96 patients will be randomly assigned across sites to 1 of 2 treatment arms, avalglucosidase alfa or alglucosidase alfa at 20 mg/kg qow in a 1:1 ratio. Randomization will be performed within each of the following 6 strata:

- A) Age <18,
- B) Age \geq 18, all genders and FVC (% predicted), Japan,
- C) Age \geq 18, male and FVC (% predicted) <55%, ex-Japan,
- D) Age \geq 18, female and FVC (% predicted) <55%, ex-Japan,
- E) Age \geq 18, male and FVC (% predicted) \geq 55%, ex-Japan,
- F) Age \geq 18, female and FVC (% predicted) \geq 55%, ex-Japan.

To control the number of patients with high baseline FVC (% predicted), the percent of enrolled patients with baseline FVC (% predicted) of 80% to 85% will be capped at 15% of the total population.

The treatment kit number lists are generated centrally by the Sponsor. The IMPs (avalglucosidase alfa or alglucosidase alfa in blinded treatment period; avalglucosidase alfa in open-label long-term follow-up period and in additional extension open-label follow-up) are packaged in accordance with the lists.

The IRT (centralized treatment allocation system) generates the patient randomization list and allocates the treatment number and the corresponding treatment kits to the patients accordingly. Investigator and assigned study site personnel will have access to blinded IRT menu/reports, whereas the unblinded pharmacist or unblinded designee will have access to unblinded reports.

The treatment kits will be allocated using a centralized treatment allocation system (IRT) every 2 weeks starting at Visit 2 (Day 1/Day 2). Multiple treatment kits will be required to be used for each IMP administration.

The number of vials of avalglucosidase alfa/alglucosidase alfa to be used for each infusion will be calculated using the latest available body weight data. Body weight will be measured at the time points specified in [Section 1.2](#).

Before randomizing a patient, the Investigator or designee will have to contact the centralized treatment allocation system/IRT.

The pediatric patients aged 3 to <18 years enrolling directly in the in the open-label long-term follow-up phase, avalglucosidase alfa will not be randomized as they will be assigned to avalglucosidase alfa.

8.5 PACKAGING AND LABELING

Packaging is in accordance with the administration schedule. The content of the labeling is in accordance with the local regulatory specifications and requirements.

8.6 STORAGE CONDITIONS AND SHELF LIFE

Investigators or other authorized persons (ie, pharmacists or designees) are responsible for storing IMP provided by the Sponsor in a secure and safe place in accordance with local regulations, labeling specifications, policies, and procedures.

Control of IMP storage conditions, especially control of temperature (eg, refrigerated storage) and information on in-use stability and instructions for handling the compound should be managed according to the rules provided by the Sponsor.

8.7 RESPONSIBILITIES

The Investigator, the hospital pharmacist, or other personnel allowed to store and dispense the IMP will be responsible for ensuring that the IMP used in the clinical trial is securely maintained as specified by the Sponsor and in accordance with applicable regulatory requirements.

All IMP will be dispensed in accordance with the Investigator's prescription and it is the Investigator's responsibility to ensure that an accurate record of IMP issued and returned is maintained.

Any quality issue noticed with the receipt or use of an IMP (deficiency in condition, appearance, pertaining documentation, labeling, expiration date, etc) should be promptly notified to the Sponsor designee. Some deficiencies may be recorded through a complaint procedure.

A potential defect in the quality of IMP may be subject to initiation of a recall procedure by the Sponsor. In this case, the Investigator will be responsible for promptly addressing any request made by the Sponsor, in order to recall the IMP and eliminate potential hazards.

Under no circumstances will the Investigator supply IMP to a third party, allow the IMP to be used other than as directed by this clinical trial protocol, or dispose of IMP in any other manner.

8.7.1 Treatment accountability and compliance

Administration of the IMP is performed in collaboration with qualified study personnel, and under the responsibility of the unblinded pharmacist or the unblinded designee.

IMP accountability:

- Unblinded pharmacist or unblinded designee will maintain records of the precise date, time of the drug administration and number of treatment units used for administration. This information can be available only to the unblinded pharmacist or unblinded designee at the site and unblinded monitor.

- The unblinded pharmacist or the unblinded designee will maintain records of the treatment numbers assigned by the central treatment allocation system/IRT at each visit.
- The unblinded monitor assigned to the study will perform reconciliation.

The patient's compliance with the treatment regimen will be monitored in terms of the patient receiving the study drug infusion qow within a ± 7 -day window from the scheduled infusion date based on V2 (Day 1/Day 2). Missed, delayed, or incomplete infusions will be clearly documented. Missed doses of study treatment due to sickness, safety concerns, or for medical reasons are not protocol deviations, but must be documented for analysis and potential impact on the study results. Refer to [Section 10.1.7](#) if the missed infusion is due to a missed visit.

8.7.2 Return and/or destruction of treatments

Destruction of IMP kits (ie, used, unused or expired) can be performed during the course of the study as well as at the end of the study once reconciliation has occurred.

Used vials must be kept in their original secondary packaging (box) unless unique treatment number is printed on the vial which will allow reconciliation to be performed by site and Sponsor representative.

In some specific cases described in the monitoring plans (blinded and unblinded), reconciliation may be performed by blinded monitor, as long as the blinding is maintained as per conditions detailed in the monitoring plan.

Reconciliation of IMP kits allocated during patient's double-blind period must be performed at the site by the unblinded pharmacist or the unblinded designee and unblinded monitor using treatment log forms and documented on-site IMP inventory countersigned by the unblinded pharmacist or the unblinded designee and unblinded monitor. A written authorization for destruction of used and unused IMP must be provided by the Sponsor once the IMP reconciliation is achieved.

Destruction at the site is strongly encouraged and can be performed provided that the following requirements are met:

- Site has appropriate facilities to destroy IMP;
- Site has procedures to allow traceability of the batches and quantities destroyed, and delivers the corresponding destruction documentation/certificate; and
- Sponsor has provided written authorization to destroy IMP.

In case the above requirements are not satisfied and the site cannot destroy IMP, the kits will be returned to Sponsor for destruction.

8.8 CONCOMITANT MEDICATION

A concomitant medication is any treatment received by the patient concomitantly to any IMP(s). Medications and therapies taken by the patient during the 30-day period prior to the

Screening/Baseline Evaluation Visit and during the course of the study will be recorded in the electronic Case Report Forms (e-CRF). Similarly, pre-infusion medications (if allowed; see [Section 8.8.1](#)) and assistive devices (eg, walker, cane, crutches) will be recorded in the e-CRF. The use (if any) of mechanical ventilation (including both invasive and noninvasive) will be recorded on the e-CRF ventilator use form.

Patients are restricted from participating in other concurrent investigational protocols that are not restricted to data and/or sample collection for patient demographic, disease and/or avalglucosidase alfa treatment purposes.

8.8.1 Pretreatment for patients with infusion-associated reactions

In clinical trials with alglucosidase alfa and avalglucosidase alfa, some patients were pretreated with antihistamines, antipyretics, and/or corticosteroids. Infusion-associated reactions occurred in some patients even after receiving antipyretics, antihistamines, or corticosteroids.

In general, the use of pretreatment in this study is at the discretion of the Investigator. The routine use of pretreatment is not recommended, especially in patients with previous immunoglobulin E (IgE)-mediated hypersensitivity reaction. Antihistamines can mask early symptoms of a hypersensitivity reaction (skin reaction), making it difficult for the infusion staff to recognize the initial signs of distress and the need to decrease the infusion rate and/or otherwise intervene.

Refer to [Section 10.6](#) for IAR management recommendations including pretreatments.

8.8.2 Prohibited concomitant medications

Use of immunomodulation treatments (eg, methotrexate, rituximab, immunoglobulins, and other immunosuppressants), either alone or in combination, that would interfere with the evaluation of the immunogenic potential of avalglucosidase alfa, is not allowed during participation in the study. In the case of administration of a prohibited treatment, the Sponsor must be notified, the treatment with IMP will be discontinued, and the patient will be asked to continue study assessments to the extent possible prior to study withdrawal.

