10.3.4 Handling of patients after permanent treatment discontinuation

Patients will be followed-up according to the study procedures specified in this protocol (see [Section 10.1.9](#)), or up to recovery or stabilization of any AE to be followed-up as specified in this protocol, whichever comes last.

Since the primary study comparison is based on intent-to-treat principle using all randomized patients with any study treatment, missing data, especially the key study assessments during the PAP (Week 49) may potentially lead to biased results and challenges in assessing the treatment effect of the study drug. Therefore, all efforts should be made to continue to follow the patients for primary and key secondary endpoints, after a permanent discontinuation of treatment, in addition to the 4-weeks post-treatment safety follow-up. At the minimum, patients should be assessed at their regularly scheduled Week 49 visit (or as close as possible to Week 49 even if it may be outside of visit window) if treatment discontinuation occurred prior to that visit.

All cases of permanent treatment discontinuation should be recorded by the Investigator in the appropriate pages of the e-CRF when considered as confirmed by documenting the reason(s) for treatment discontinuation.

Patients who permanently discontinue study treatment and who will be switched to commercial avalglucosidase alfa will be withdrawn from the study.

In the event that a patient dies, permission will be sought (through a separate informed consent form) for a research autopsy or post mortem research biopsy. Samples collected from these procedures will be used for research purposes only and data will not be included in any study analyses.

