10.6 SAFETY INSTRUCTIONS

For management of mild IARs, infusion rate reductions (ie, reduced to half the rate) or temporary interruptions may mitigate the reaction.

Testing for moderate, severe, and recurrent mild IARs will include, if clinically indicated:

- Assessments for circulating immune complex detection; and IgE, serum tryptase, and complement activation, following moderate, severe, or recurrent mild IARs suggestive of hypersensitivity reactions.
- Skin testing if IARs are suggestive of a type I hypersensitivity reaction (IgE-mediated) as appropriate.

For moderate to severe or recurrent IARs, the Investigator may consider the use of pretreatment medications (ie, antihistamines, antipyretics, and/or glucocorticoids), in addition to infusion rate reductions, interruptions, or even discontinuation, if necessary. Please refer to the IB (Sections 7.1.2 and 7.1.3) for further guidance on the management of IARs.

Moderate, severe, and recurrent mild IARs will be discussed with the DMC. If the DMC recommends or suggests that a desensitization procedure to the IMP could be proposed to the patient, in agreement with the Investigator, such a procedure may be initiated as per pharmacy manual guidelines. Depending on the phase of the study the patient will be in at the time of the desensitization procedure, this one may be blinded (if the procedure is started when the patient is still in the double-blind phase) or unblinded (if the procedure is started when the patient is in one of the open-label phases).

If severe hypersensitivity or anaphylactic reactions occur, immediate discontinuation of the infusion should be considered, and appropriate medical treatment should be initiated. Severe

reactions are generally managed with infusion interruption, administration of antihistamines, corticosteroids, IV fluids, and/or oxygen, when clinically indicated. In some cases of anaphylaxis, epinephrine has been administered. Because of the potential for severe infusion reactions, appropriate medical support measures, including cardiopulmonary resuscitation equipment especially for patients with cardiac hypertrophy and patients with significantly compromised respiratory function, should be readily available.

The Investigator will continue to monitor the patient until the parameter returns to baseline or until the Investigator determines that follow-up is no longer medically necessary.

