1.2 OBJECTIVES

1.2.1 Primary objectives

The primary objective of the study is to determine the effect of avalglucosidase alfa treatment on respiratory muscle strength as measured by FVC % predicted in the upright position, as compared to alglucosidase alfa.

Estimand for this study is defined as the difference between avalglucosidase alfa treatment and alglucosidase alfa in mean FVC % predicted change from baseline to Week 49 regardless of whether intercurrent events have occurred. This estimand corresponds to a ‘treatment policy strategy’.

Analysis method for estimand (estimator) is based on mixed model for repeated measures (MMRM) assuming missing at random (MAR). All observed data during the study that include the data collected after study treatment discontinuation will be used in the analyses.

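### Protocol 8.8.2 presupposes study withdrawal after a prohibited immunomodulator and sets no Week 49 minimum, in tension with the protocol's own follow-up rules and the treatment-policy estimand

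*Protocol*

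**What the plan says.** Protocol 8.8.2 bars "Use of immunomodulation treatments (eg, methotrexate, rituximab, immunoglobulins, and other immunosuppressants), either alone or in combination", where the treatment is one "that would interfere with the evaluation of the immunogenic potential of avalglucosidase alfa". If such a treatment is given, the sponsor is told, study drug is stopped, and "the patient will be asked to continue study assessments to the extent possible prior to study withdrawal".

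Other sections deal with patients who are off study drug for any reason:

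- Protocol 8.1: patients who stop treatment early are followed on the normal schedule.
- Protocol 9.1.1: pulmonary function is still collected to at least Week 49.
- Protocol 10.1.9: efficacy and safety assessments off treatment fall at Weeks 13, 25, 37 and 49.
- Protocol 10.3 and 10.3.5: the patient stays in the study for as long as is feasible, and stopping study drug is kept distinct from withdrawing consent to follow-up.
- Protocol 10.3.4: "all efforts should be made to continue to follow the patients for primary and key secondary endpoints, after a permanent discontinuation of treatment". The Week 49 visit is the minimum, even outside its window, and the section warns that missing Week 49 data could bias the result.

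SAP 1.2.1 defines the estimand as the difference between arms "in mean FVC % predicted change from baseline to Week 49 regardless of whether intercurrent events have occurred", which it labels a treatment policy strategy. The estimator is an MMRM under missing at random that uses all observed data, including data collected after treatment stops.

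**The concern.** A treatment-policy estimand can be estimated as intended only if outcomes are collected after the intercurrent event. Section 8.8.2 covers one such event and handles follow-up more weakly than the rest of the protocol: assessments are a matter of best effort, and leaving the study is assumed. A site that looks up only this section could end follow-up before Week 49 and believe it had complied.

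The stated purpose of the ban is to protect the evaluation of immunogenicity. That purpose gives no reason to stop measuring FVC.

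At stake is avoidable missing data that may be informative. Immunomodulators might be given after antibody or infusion reactions, and those could differ between the two enzymes. The documents say neither, so this is an assumption. If it holds, the missing values would not sit comfortably under missing at random. The tipping-point analysis in SAP 2.5.3.1 probes that assumption, but it runs only if non-inferiority is shown and cannot supply values that were never measured. A patient without a valid Week 49 FVC also leaves the per-protocol set (SAP 2.3.1.2).

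**Working it through.** **Step 1. The rules side by side.**

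| Question | 8.8.2 | 8.1, 9.1.1, 10.1.9, 10.3, 10.3.4 |
|---|---|---|
| Are assessments continued off study drug? | Yes, as far as can be managed | Yes, on a set schedule |
| Minimum follow-up? | None stated | Week 49 |
| Is study withdrawal expected? | Yes, with no date | No; the patient is kept in the study |
| Pointer to the off-treatment rules? | None | 10.1.9 and 10.3.4 are those rules |

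Section 8.3.2 is a useful comparison. Breaking the code also ends dosing, but that section sends the site to 10.3. Section 8.8.2 does not.

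**Step 2. The plan's own sample size.** Inputs from Protocol 11.1: SD 5.1, true difference 2.0, margin 1.1, two-sided 5%, 80% power, 10% missing.

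- n per arm = 2 × (1.960 + 0.842)² × 5.1² / (2.0 + 1.1)² = 42.5, so 43 per arm and 86 evaluable.
- 86 / (1 − 0.10) = 95.6, so 96 randomized.
- Power by the noncentral t with 43 per arm is 79.6%, which matches SAP Table 4.

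No figure in the plan needs correction.

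**Step 3. Scale of one patient.** 1/48 = 2.1% of an arm. The missing-data allowance is 0.10 × 48 = 4.8 patients per arm, so one patient uses about a fifth of it.

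**Step 4. Power after further losses.** The number lost is assumed, counted beyond the planned 10% and split evenly between arms.

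| Further Week 49 values lost | Evaluable | Non-inferiority power |
|---|---|---|
| 0 | 86 | 79.6% |
| 1 | 85 | 79.1% |
| 2 | 84 | 78.6% |
| 4 | 82 | 77.6% |
| 8 | 78 | 75.5% |

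**Step 5. Possible shift in an arm mean.** Suppose m patients in one arm of 48 are lost and their true change is d points worse than a missing-at-random model predicts. The arm mean is then too favourable by about m × d / 48. Both m and d are assumed.

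- m = 1, d = 2: 0.04 points
- m = 1, d = 5: 0.10 points
- m = 4, d = 5: 0.42 points

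The margin is 1.1 points. One such patient hardly matters. Four in a single arm with a large departure would, but four is close to that arm's whole allowance of 4.8.

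**The case against.** The best defence is that 8.8.2 does not order anyone out. The same sentence asks for continued assessments and gives no date for leaving. Where the protocol means to require withdrawal it says so directly, as in 10.3.4 for patients who switch to commercial product. The follow-up rules make no exception for prohibited medication, so a careful site would read the sections together and bring the patient back at Week 49. This stands in part. The conflict is one of wording, and nothing in 8.8.2 forbids Week 49 data. It does not remove the problem, because the section a site would consult for this event neither states the Week 49 minimum nor refers to where it is stated.

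Two stronger readings are tempting, and the documents support neither.

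- A reader might infer that stopping study drug itself breaches the estimand. It does not. A treatment-policy estimand accommodates treatment discontinuation, and the SAP uses data collected afterwards. Only the assumed exit from the study is in tension with it.
- A reader might infer that 8.8.2 contradicts the glucocorticoid pretreatment allowed elsewhere. It does not name corticosteroids and limits the ban to treatments that would interfere with the immunogenicity evaluation. Section 8.8.1 leaves pretreatment to the investigator, and 10.6 expressly mentions glucocorticoids for moderate to severe or recurrent reactions. At most, no explicit carve-out is written.

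Timing also counts. Amended protocol 06 is dated February 2022 and reports the last enrolment in August 2020. Week 49 falls 48 weeks after the first infusion, so it had passed for every patient by about mid-2021. Rewording this version cannot recover Week 49 data.

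**Conclusion.** The point holds as a drafting inconsistency with a possible consequence for the data. Section 8.8.2 treats withdrawal as the expected outcome of a prohibited treatment and sets no minimum follow-up, while the other sections and the SAP estimand call for Week 49 FVC whatever has happened to study drug. A site following 8.8.2 literally may fail to collect that value.

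The size is modest and cannot be fixed from the documents, which give no expected number of cases. Power is barely affected. The worry is avoidable missing data that may depend on treatment and tolerability, and that dependence is an assumption. The conclusion also assumes that the present text of 8.8.2 was in force during the blinded period. The amendment history lists no change to it, but minor edits were not itemised.

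**What to change.** In 8.8.2, replace the closing phrase about best-effort assessments before withdrawal with follow-up under 10.1.9 and 10.3.4 through at least Week 49, so that a prohibited medication is not by itself a reason to leave the study. Leave other withdrawal rules as they are. Making withdrawal of consent the only route out would go too far, because it would clash with the withdrawal in 10.3.4 of patients who switch to commercial product.

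Which treatments are prohibited, and when study drug stops, remain for the sponsor to decide.

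The cost is a wording change in one section. No visits are added, because the off-treatment schedule already exists. For patients already past Week 49, the summaries by reason for dropout planned in SAP 2.5.3.1 can be used to check whether any FVC values were lost this way.
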